## 6. Overview of intervention and comparison facilities

The program interventions are implemented in 8 NGO-run urban health facilities, 4 of which are operated by Radda and 4 of which are operated by Marie Stopes. These 8 facilities will serve as the intervention group. The comparison group will also consist of 8 NGO-run urban health facilities, but these are run by Nari Maitree and Shimantik, which operate under the Urban Primary Health Care Services Delivery Project. The list of facilities in the intervention and comparison groups is presented in **Appendix 1**.

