## 7. Sample size and power calculation

Sample size has been estimated based on the baseline prevalence of the primary outcomes, the expected change after intervention, the power to detect those differences at 0.80, and a level of significance of 0.05. The outcomes used for sample size calculation were quality of nutrition service delivery (including provision of counseling on diet and breastfeeding practices). The sample size was calculated at 2 levels: provision of services (measured through case observation) and receipt of services (measured through client interviews).

Based on data from baseline assessment, we calculated the prevalence for expected outcomes, and the intra-cluster correlations (ICCs). We estimated that a minimum sample size of 1200 clients per group during the first phase of the endline survey conducted at the facilities would have at least 80 percent power to detect a difference of 10-19 percentage points (pp) between intervention and comparison groups in the changes over time for different context-specific outcomes (**Table 2**), e.g. maternal counselling during pregnancy and IYCF counselling to caregivers of young children. During the follow up in the communities, we expect a ~30-33% loss from the original sample, and thus estimate we will collect information from 65-70%. We expect that this will give us enough power to detect changes in context-specific behavioral outcomes. Instead of separating the sample for ANC and child contacts, we will pool them to examine context-appropriate behavior such as pregnant women with dietary diversity/IFA and calcium consumption and caregivers with age-appropriate child feedings. These detectable differences are of reasonable public health significance and based on the previous experience from evaluation of the A&T Bangladesh maternal nutrition study [7].

For facility readiness and provider knowledge, with the sample size of 8 facilities and 40-64 providers in this group, we will mainly report the descriptive analyses between two groups, but not report statistical test due to small sample size.

Table 2. Sample size and power calculation

	Control group, endline 	Expected difference	Treatment group, endline	Power	ICC	Alpha	Sample size per group
Quality of services (measured through case observation)							1200
Counseling on diet	68.0	19.0	87.0	0.8	0.103	5	
Counseling on breastfeeding	71.6	17.1	88.7	0.8	0.09	5	

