Context-appropriate behavioral outcomes (measured through client interview)							1200 at facility-based endline 800 (67%) at community-based endline
Consume 100+ IFA	54.5	9.5	64.0	0.8	0.001	5	
Dietary diversity during pregnancy	74.0	9.5	83.5	0.8	0.009	5	
Early initiation of breastfeeding	32.8	13.5	46.3	0.8	0.024	5	

Data from AINNS study [8]

Data from Bangladesh DHS 2014 [9]

We expect to see no difference in the control group at baseline vs. endline.

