- Pregnant women who are visiting the health facilities for ANC visits (at least twice during her pregnancy, around half of clients)
- Mothers with children <12 months of age who are visiting the health facilities for health check-ups or vaccination

Exclusion criteria:

- Pregnant women with severe illness or complications
- Mothers with severely ill children

For the assessment of **impacts** of standardized and upgraded MIYCN counseling service on coverage and behavior changes we will identify each facility's catchment area and find women in the community who accessed services at those health facilities to sample 1600 facility clients (PW and RDW) to interview (**Table 4**). During the facility interviews, we will seek their consent to be interviewed at home for the community

interview at a later time. Follow-up with clients for the community interview was conducted within 3 months following the facility interview at baseline. At endline, facility clients will be visited within one month to conduct the community interview. We expect that we will be able to follow 65-70% of these women. By doing so, we ensure that our clients will have at least one visit in the evaluation facilities (both intervention and control areas). We can track the number of clinic visits and thus conduct the dose response analysis.

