**Table 7. Modules included in client interview**

Module	Topic	Description
1	Background and demographic characteristics	Factors such as age, education, religion, living standard, etc., have influences on client's behaviors, including MIYCN practices and service utilization. This data also provides information about outside factors, including the COVID-19 pandemic that may constrain mothers' ability to benefit from services. Data will be collected on household information, socioeconomic status, income and expenditure, and the education and other characteristics of the women and their husbands.
2	Obstetric history	This section information on the woman's pregnancy history including complications, total parity and age at first parity.
3	Previous ANC care/care seeking for the child	This will include receipt and consumption of IFA and calcium and antenatal care and counselling during current pregnancy for pregnant women. Mothers of sick children will also be asked about postnatal services, morbidity and care of children, and vaccination history. This will help to assess if exposure to

Module	Topic	Description
		intended program is occurring as expected and assess impact trends by levels of exposure to interventions.
4	MN Dietary intake/IYCF practices	Respondents will be asked to recall what they ate (ANC clients) or what they fed their children (mothers of sick children) on the previous day. Mothers of sick children will also be asked other questions on IYCF practices and behaviors. This will provide information on MIYCN behaviors.
5	Current MIYCN knowledge and perceptions	Data on mothers' MIYCN knowledge and perceptions can be used to assess trends in impact indicators and to identify pathways to positive behavior change. Questions on self-efficacy will be included.
6	Social desirability	This is a factor that may affect the woman's ability to change behaviors and practices around MIYCN.
7	Food security	Questions on food security will be included as they are related to the respondent's ability to follow counselling on diet for herself and her children.
8	Decision-making power and mental health	Decision-making power and mental health are also related to the woman's ability to change behaviors and practices around MIYCN.

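### Early initiation of breastfeeding rests on mothers whose only guaranteed facility visit follows the outcome, and its power at the 400 child-contact interviews per group is about 76%, not 80%

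*Combined protocol and SAP*

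**What the plan says.** Section 4 lists early initiation as a secondary outcome. Table 2 (Section 7) gives "Early initiation of breastfeeding" a control level of 32.8%, an expected difference of 13.5 pp and an ICC of 0.024. Section 7 sets "a level of significance of 0.05" and "the power to detect those differences at 0.80". The behavioural block of Table 2 carries 1200 per group at the facility round and "800 (67%) at community-based endline". Section 7 also says that ANC and child contacts are pooled for the behavioural outcomes.

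Section 8 recruits two kinds of client: pregnant women attending ANC, and "Mothers with children <12 months of age who are visiting the health facilities for health check-ups or vaccination". A condition on repeat ANC visits is attached to the pregnant women only. Because clients are recruited at a facility, the plan notes that each has had one visit or more there, and it proposes a dose-response analysis on the number of visits (Sections 8 and 9.4). Endline home follow-up is within one month. Table 4 splits the endline client interviews into 400 ANC and 400 IMCI (child-contact) clients per group.

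In Table 7, module 3 covers "antenatal care and counselling during current pregnancy for pregnant women". For mothers of sick children it adds postnatal services, child illness and care, and vaccination history.

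**The concern.** Whether a mother puts the baby to the breast early is settled around delivery. With home follow-up within a month, few of the women recruited while pregnant could report it for that pregnancy. The plan does not name who supplies the outcome, but in effect it is the child-visit mothers, with a child aged anywhere from 0 to under 12 months. The visit that brings them into the study cannot have changed it. Section 4 justifies the under-12-month window by exposure at immunization contacts, which suits current feeding but again falls after birth.

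Two things are at stake. First, if many of these mothers had no program contact before delivery, a null result could not distinguish an ineffective program from one that did not reach them in time. A dose-response analysis on total visits would misclassify exposure for this outcome, because visits after birth would count as dose. Second, the 800 per group in Table 2 includes pregnant women who mostly cannot contribute, so the printed power does not describe the sample that can be analysed.

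**Working it through.** **Inputs from the documents.** p1 = 0.328, p2 = 0.463, d = 0.135 and ICC = 0.024 (Table 2). Alpha is 0.05, taken as two-sided because the plan does not say. There are 8 facilities per group (Section 6: "These 8 facilities will serve as the intervention group", with 8 comparison facilities). n = 800 per group is from Table 2, and n = 400 child-contact interviews per group from Table 4. The comparison is endline only, as Table 2 is laid out.

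**Formulas.** Design effect DE = 1 + (n/8 − 1) × ICC. Effective size n_eff = n/DE. With p̄ the mean of p1 and p2,

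power = Φ{[d√n_eff − 1.96√(2p̄(1 − p̄))] / √(p1(1 − p1) + p2(1 − p2))}.

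**Step 1: the plan's own figure.** At n = 800, DE = 1 + 99 × 0.024 = 3.376 and n_eff = 237.0. The two square-root terms are 0.6915 and 0.6849. Then (0.135 × 15.394 − 1.96 × 0.6915)/0.6849 = 1.056, so power = 0.854. A t reference with 14 degrees of freedom gives 0.805. The text's claim of 80 percent or more is therefore met at 800, although no single method I tried reproduces all five rows of Table 2.

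**Step 2: the sample that can report the outcome.** At n = 400, DE = 1 + 49 × 0.024 = 2.176 and n_eff = 183.8. Then (0.135 × 13.558 − 1.96 × 0.6915)/0.6849 = 0.694, so power = 0.756 (0.701 with the t reference). The smallest difference detectable with 80% power is 14.3 pp, against 12.5 pp at 800. About 520 child-contact mothers per group would be needed for 80% power at 13.5 pp.

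**Step 3: dilution.** The share f of mothers reached before birth is not in the documents. Assume, for illustration, 13.5 pp in those reached and zero in the rest, so the average difference is 13.5 × f.

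| Share reached, f | Average difference | Power, n = 800 | Power, n = 400 |
|---|---|---|---|
| 100% | 13.5 pp | 0.85 | 0.76 |
| 75% | 10.1 pp | 0.62 | 0.52 |
| 50% | 6.75 pp | 0.33 | 0.27 |
| 25% | 3.4 pp | 0.12 | 0.10 |

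At 800, power stays at 0.80 or above down to f of about 93%. At 400 it is below 0.80 even at f = 100%. Conversely, for the average over all mothers to be 13.5 pp with half of them reached, the effect in those reached would have to be 13.5/0.5 = 27 pp.

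**The case against.** Several stronger readings are tempting, and the documents do not support them.

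- A reader might infer that the 13.5 pp is certainly diluted. Section 7 says only that the differences draw on an earlier evaluation of a related program. The figure may already be an average over all sampled mothers, in which case nothing is left to dilute. Step 3 is conditional and shows a range, not an estimate.
- A reader might infer that the 80% power holds only if every mother had ANC at the facility. Steps 1 and 3 show otherwise: at 800 there is some slack, and at 400 the target is missed even with full exposure.
- A reader might infer that only facility ANC could have reached these women in time. Table 1 also lists community workers, flyers, satellite outreach at one NGO's facilities and ANC camps at the other's. Their reach is not given. Phone education ended in November 2020, so it would touch few pregnancies leading to children under 12 months in May and June 2022.
- A reader might infer from module 3 that mothers will not be asked about earlier ANC. Its title covers previous ANC, its text says mothers will be asked *also* about postnatal matters, and Table 7 is a summary, not the questionnaire. What can be said is that the item is not listed for them.
- Restricting the outcome to mothers with ANC at the facility looks like a natural remedy. But the program promotes facility visits and utilization is a primary outcome, so this would select on something the intervention may change.

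It can also be said that if early initiation were asked of all 600 child-contact clients observed per group at the facility, power would be 0.82. Section 9, however, places the measurement of behaviours in the community round. Finally, this is one secondary outcome, and Section 10 does not name it individually.

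These points limit the claim. They leave three gaps standing: the guaranteed visit follows the outcome, the dose count ignores timing, and 800 is the wrong sample size for this row.

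**Conclusion.** The concern holds in a limited form. The order of outcome and guaranteed visit, the lack of any rule on earlier contact, and the undivided visit count follow from Sections 8 and 9.4. That child-visit mothers supply the outcome is inferred from the follow-up interval.

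The firm numerical result is that the Table 2 row is overstated for its own sample: about 0.76 for 13.5 pp at 400 per group, using the plan's ICC, 8 facilities per group and a two-sided normal approximation. The direction of any dilution is clear, but its size is not derivable from the documents. It ranges from none to a power of 0.10 at 400 per group with 25% reached, under the zero-effect assumption for the rest. This is an inexpensive improvement to a secondary outcome together with one power figure that needs correcting. It does not threaten the primary objectives.

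**What to change.** 1. Make sure the mothers' questionnaire records ANC visits at the study facility, and other program contact (community worker, outreach, ANC camp), before the index birth.
2. State that all child-contact mothers form the main denominator for early initiation. Pre-specify a secondary analysis by prenatal exposure, to be read with caution because the program may itself alter attendance. That analysis will be small: if half of the 400 are exposed, 200 per group give power of about 0.60 for 13.5 pp.
3. For this outcome, count only visits before birth in the dose-response analysis.
4. Restate the Table 2 row for 400 child-contact mothers per group (power about 76%, minimum detectable difference about 14.3 pp), over a range of exposed shares, and say whether 13.5 pp is meant for mothers reached or for all mothers.

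The cost is one questionnaire item, a less favourable power figure, and a baseline contrast limited to what the baseline asked. The protocol is dated October 1, 2021. Section 11 schedules questionnaire preparation for November 2021 to January 2022 and data collection for May and June 2022, so the changes fit the timetable.

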## 8. Sampling and enrollment of study subjects

**Sampling providers:** The program interventions are implemented in 8 NGO-run health facilities in Dhaka, with another 8 serving as comparison facilities; thus, 16 facilities will be included in the survey. From each facility, we will interview 6-8 health providers (1 medical officer or 1 paramedic, 1-2 counselors, and 3-4 community workers) (**Table 3**). We expect that the number of counselors across facilities may differ; counselors may already be present at some intervention and comparison facilities prior to the intervention. Therefore, 1 counselor may be interviewed at comparison facilities, and 1-2 counselors (1 existing counsellor and 1 additional A&T MIYCN Counselor) may be interviewed at intervention facilities. Similarly, dedicated Community Workers hired by A&T will be available at intervention facilities but not at comparison facilities. Due to the small numbers of Program Managers (n=2) and Field Supervisors (n=4), we plan to conduct in-depth interviews with them to obtain some additional insights on overall intervention impact pathway, uptake of interventions, program performance and supportive supervision activities.

Table 3. Sampling healthcare personnel at intervention and comparison facilities

Levels		Intervention facilities (n=8)	Comparison facilities (n=8)
Baseline	Permanent facility personnel		
	Medical officer	1	1
	Counsellor	1	1
	Paramedic	1	1
	Community worker	3	3
	Total:	N=48	N=48
Endline: Quantitative survey	Permanent facility personnel		
	Medical officer	1	1
	Counsellor	1	1
	Paramedic	1	1
	Community worker	3	3
	A&T temporary hiring		
	MIYCN Counsellor	1	0
	Community Worker	1	0
	Total:	N=64	N= 48
Endline: Qualitative in-depth interview	Program Manager	2	0
	Field Supervisor	4	0
	Total:	N=6	N=0

**Sampling clients:** At each health facility, 4 intervals of time (8-10 AM, 10AM-12PM, 1-3 PM and 3-5 PM) will be chosen. Pregnant women or children visiting the facility within these 4 selected intervals will be randomly selected (in proportion to the case load in each interval) for interview and observation. We plan to sample 10 clients each day from each facility (5 pregnant women and 5 mothers with children <12 months).

The inclusion criteria for recruiting clients are as follows:

- Pregnant women who are visiting the health facilities for ANC visits (at least twice during her pregnancy, around half of clients)
- Mothers with children <12 months of age who are visiting the health facilities for health check-ups or vaccination

Exclusion criteria:

- Pregnant women with severe illness or complications
- Mothers with severely ill children

For the assessment of **impacts** of standardized and upgraded MIYCN counseling service on coverage and behavior changes we will identify each facility's catchment area and find women in the community who accessed services at those health facilities to sample 1600 facility clients (PW and RDW) to interview (**Table 4**). During the facility interviews, we will seek their consent to be interviewed at home for the community

interview at a later time. Follow-up with clients for the community interview was conducted within 3 months following the facility interview at baseline. At endline, facility clients will be visited within one month to conduct the community interview. We expect that we will be able to follow 65-70% of these women. By doing so, we ensure that our clients will have at least one visit in the evaluation facilities (both intervention and control areas). We can track the number of clinic visits and thus conduct the dose response analysis.

**Table 4. Sampling clients at intervention and comparison facilities**

Levels		Intervention facilities (n=8)	Comparison facilities (n=8) 
Baseline	Case observation		
	ANC	600	100
	IMCI	600	100
	Client interview		
	ANC	400	70
	IMCI	400	70
	Total:	2,000	340
Endline	Case observation		
	ANC	600	600
	IMCI	600	600
	Client interview		
	ANC	400	400
	IMCI	400	400
	Total:	2,000	2,000

#### **Informed consent**

Written consent will be obtained from both clients and providers using informed consent forms. These forms are available in both English and Bengali, and clearly explain the purpose of the research, how the collected data will be used, why the respondent has been selected, interview process, risks and benefits, and steps to ensure the privacy, anonymity and confidentiality of the collected information. All COVID-19 transmission risks to study participants and the precautionary measures that will be followed during data collection to limit the risk of transmission will be included in the informed consent. The respondent's right to withhold consent or withdraw at any time, as well as contact details for questions about the study, are clearly outlined. These details will be mentioned verbally to the respondent to ensure comprehension.

## 9. Data collection methods

The survey will use mixed data collection methods including: 1) facility assessment; 2) provider survey; 3) case observations (include ANC visits, child visits [both sick child and immunization], and counseling session), 4) client interviews, and 5) in-depth interview with Program Managers and Field Supervisors. At endline, we will have two rounds of client interviews: one round at the health facility to measure utilization and one round to follow up clients (within a months later) in the community to measure behavior changes.

### 9.1. NGO-run urban health facility assessment

The urban health facility assessment will be conducted at baseline and endline for 8 intervention and 8 comparison health facilities. The health facility questionnaire will contain modules related to facility infrastructure (both in terms of overall organization as well as basic amenities), services provided to women and children (either at the facility or through outreach activities), service readiness, case load, and availability of trained providers. Additional questions will focus on identification and tracking of clients and the catchment area for the facility (**Table 5**).

There are two components to the urban facility assessment:

- Interview with the manager of the facility to obtain information on available personnel and services offered. Data were also gathered from monitoring forms to assess utilization and coverage of MIYCN-related services.
- A facility observation checklist will be included to obtain information on the counseling room or space. A predefined checklist will be developed to document the presence and condition of infrastructure, equipment, supplies and information, education and communication (IEC) materials in the counseling area.

**Table 5. Modules included in the urban facility assessment**

Module	Topic	Description
1	Characteristics of facility	Identification, location, type, provision of in-patient or outpatient care, catchment areas
2	Facility infrastructure	Overall organization and basic amenities
3	Service readiness of facility	Including availability of counseling room, functional nutrition supplies, logistics, drugs, IEC materials
4	Services provided	Serviced provided either at facility or through outreach including nutrition services for pregnant women, immunization, well-child care, sick under-5 children, SAM/MAM management
5	Caseload	Case load for ANC, immunization, sick child, SAM/MAM, supplementation, referrals, counselling
6	Human resources	Availability of trained providers and their qualification
7	Monitoring system	How the facility monitors and track clients

## 9.2. Provider survey

The provider survey will be conducted at baseline and endline. Modules for the provider questionnaire will include provider characteristics, workload and time commitments for services provided, exposure to training, knowledge (both theoretical and application based), motivation and self-efficacy, and incentives and remuneration (**Table 6**).

